2.7 Center and Country Effect

Not applicable since this is a single-center study.

2.8 Handling Missing Data

Generally, missing values of immunogenicity variables will not be imputed, and the analysis will be limited to observed values. For missing data in AE evaluation concerning seriousness, severity or causality a worst case approach will be applied. In case of missing assignment to solicited or unsolicited, this AE will neither be counted in tables for solicited AEs nor in tables for unsolicited AEs but in tables for all AEs.

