12.7 Missing Data

All attempts will be made to prevent missing data and generally, missing will not be imputed, and analysis will be limited to observed values. However, for missing data in AE evaluation (e.g. missing information about severity or causality) a worst-case approach will be applied.

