1. OVERVIEW

1.1 Study Design

MV-CHIK-205 is a prospective, interventional, observer blinded, block-randomized phase II trial, comparing different dose levels of MV-CHIK in three different formulations ((lyophilized, liquid frozen and liquid Stabilizing and Protecting Solutions (SPS®)) to evaluate immunogenicity, safety and tolerability of this novel Chikungunya vaccine in 60 healthy volunteer female and male subjects. Placebo (physiological saline solution) will be applied to blind two different treatment schedules, evaluating single shot versus double shot treatment. The study will be conducted as a single study site.

After completion of screening procedures, subjects will be randomized to one of five treatment groups (A, B, C, D or E) and will receive injections according to the scheme outlined in the study flow chart (see [Section 1.5](#)).

Group A: 12 subjects will receive two low dose treatments with MV-CHIK 5×10^4 (± 0.5 log) TCID50 /dose on day 0 and 28 (lyophilized formulation).

Group B: 12 subjects will receive two low dose treatments with MV-CHIK 1×10^5 (± 0.5 log) TCID50 /dose on day 0 and 28 (liquid frozen formulation).

Group C: 12 subjects will receive two low dose treatments with MV-CHIK 1×10^5 (± 0.5 log) TCID50 /dose on day 0 and 28 (liquid SPS® formulation).

Group D: 12 subjects will receive two high dose treatments with MV-CHIK 1×10^6 (± 0.5 log) TCID50 /dose on day 0 and 28 (liquid frozen formulation).

Group E: 12 subjects will receive one high dose treatment with MV-CHIK 1×10^6 (± 0.5 log) TCID50 /dose on day 0 (liquid frozen formulation) and placebo on day 28.

Subjects will be observed for safety and immunogenicity for 56 days during the treatment period, starting with the first MV-CHIK vaccination at day 0 (Visit 1), day 14 (Visit 2), day 28 (Visit 3), day 42 (Visit 4) and day 56 (Visit 5). After this treatment period subjects will return to site at day 182 (Visit 6) and at day 365 (Visit 7) for collection of serum to follow up the durability of specific antibodies against Chikungunya. Serum samples for passive transfer will be collected on days 0, 28, 56 and 365.

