1.3.2 Secondary Endpoints

- Rate of solicited and unsolicited adverse events (AEs) during the treatment period until day 56
- Serious adverse events during the treatment period until study day 56
- Immunogenicity on days 0, 28 (group A, B, C, and D), days 0, 56 (group E) and long-term immunogenicity on day 182 (6 Month) and 365 (12 Month), confirmed by the presence of functional antibodies as determined by the plaque reduction neutralization test (PRNT₅₀).
- Measurement of anti-Chikungunya antibodies on days 0, 28, 56, 182 and 365 determined by enzyme linked immunosorbent assay (ELISA)
- Measurement of anti-Measles antibodies on days 0, 28, 56 determined by enzyme linked immunosorbent assay (ELISA)

Adapted from:

STAT03_A Statistical Analysis Plan

Version 6.0, Effective Date 16-Feb-2018

Confidential and intellectual property of Assign DMB. No part of this document or its contents may be duplicated, referenced, published or otherwise disclosed in any form or by any means without prior written consent of Assign DMB.

Page 7 of 29

[figure not shown]
06CJDX

- Induction of Chikungunya specific immune responses on days 0, 14, 28, 42 and 56 determined by T-cell assay.
- Safety laboratory parameters (hematology, serum chemistry, coagulation, urinalysis)

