6.2.2 Derivations and Definitions

- All solicited and unsolicited Adverse Events up to day 56 (Visit 5) will be analyzed for the preliminary analysis. AE reporting and documentation is completed at Day 56. Thus all AE in the database are considered for the adverse event endpoints. In case of unexpected data change, new reported AEs or follow-up information, affected tables and/or listings may be repeated for the final analysis. Otherwise,

Adapted from:

STAT03_A Statistical Analysis Plan

Version 6.0, Effective Date 16-Feb-2018

Confidential and intellectual property of Assign DMB. No part of this document or its contents may be duplicated, referenced, published or otherwise disclosed in any form or by any means without prior written consent of Assign DMB.

Page 16 of 29

06CJDX

adverse event tables are not repeated at the final analysis. This decision may be done in a DRM prior to database closure, see [Section 2.9](#).

- Percentages for AE rates are based on N (treatment group totals).
- Medical Conditions/symptoms noted prior to first IMP administration will be reported as medical history and not as adverse events. In case of an incomplete start date where it cannot clearly be decided if the Adverse Event started before the first IMP the Adverse Event will be considered to be started before first IMP.
- An Adverse Events is considered to be related to study treatment if “Relationship to Study Treatment” is answered with “definitely”, “probably” or “possibly” or the causality is missing.
- Adverse Events where an action was taken are considered if “Action taken with Study Treatment” is answered with “Second IMP Administration Delayed” or “Second IMP not Administered”.
- Tables showing “severe” events will include events with grade 3 or 4 or missing grade.
- In tables showing subjects with AEs by maximum severity, subjects will be counted only in the highest grading category, but events will be counted in each reported grading category.
- In tables showing AEs by causality, subjects will be counted only in the strongest relationship category, but events will be counted in each category.

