1.4.18	n/a	Subjects with related severe unsolicited Adverse Events by SOC and PT (Safety Population)	
1.4.19	n/a	Subjects with related serious unsolicited Adverse Events by SOC and PT (Safety Population)	
1.4.20	n/a	Subjects with related medically attended unsolicited Adverse Events by SOC and PT (Safety Population)	
1.4.21	n/a	Subjects with unsolicited Adverse Events leading to second Vaccination not administered (Safety Population)	
1.4.22	n/a	Subjects with unsolicited Adverse Events caused study discontinuation (Safety Population)	
1.4.23	n/a	Subjects with at least one unsolicited Adverse Event by Maximum Severity (Safety Population)	
1.4.24	n/a	Subjects with at least one medically attended unsolicited Adverse Event by Maximum Severity (Safety Population)	
1.4.25	n/a	Subjects with at least one unsolicited Adverse Event by Causality (Safety Population)	
1.4.26	n/a	Subjects with at least one medically attended unsolicited Adverse Event by Causality (Safety Population)	
1.4.27	n/a	Subjects with at least one serious unsolicited Adverse Event by Causality (Safety Population)	
Laboratory Parameters			
1.4.28	n/a	Absolute Values for Hematology Parameters by Parameter and Visit (Safety Population)	
1.4.29	n/a	Absolute Values for Clinical	

Adapted from:

Page 24 of 29

STAT03_A Statistical Analysis Plan

Version 6.0, Effective Date 16-Feb-2018

Confidential and intellectual property of Assign DMB. No part of this document or its contents may be duplicated, referenced, published or otherwise disclosed in any form or by any means without prior written consent of Assign DMB.

06CJDX

		Chemistry Parameters by Parameter and Visit (Safety Population)	
1.4.30	n/a	Absolute Values for Coagulation Parameters by Parameter and Visit (Safety Population)	
1.4.31	n/a	Absolute Changes from Baseline for Hematology Parameters by Parameter and Visit (Safety Population)	
1.4.32	n/a	Absolute Changes from Baseline for Clinical Chemistry Parameters by Parameter and Visit (Safety Population)	
1.4.33	n/a	Absolute Changes from Baseline for Coagulation Parameters by Parameter and Visit (Safety Population)	
1.4.34	n/a	Subjects with Hematology Parameters Outside Normal Range by Parameter and Visit (Safety Population)	
1.4.35	n/a	Subjects with Clinical Chemistry Parameters Outside Normal Range by Parameter and Visit (Safety Population)	
1.4.36	n/a	Subjects with Coagulation Parameters Outside Normal Range by Parameter and Visit (Safety Population)	

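### An adverse event with no solicited/unsolicited flag is left out of both sets of tables, so one secondary AE rate can be understated and a serious event's term can go untabulated

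*Combined protocol and SAP*

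**What the plan says.** SAP 2.8 treats two kinds of gap in an AE record differently.

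- For three items it fills the gap conservatively: "For missing data in AE evaluation concerning seriousness, severity or causality a worst case approach will be applied". SAP 6.2.2 carries this through, counting a missing grade as severe and a missing causality as related.
- For a missing solicited/unsolicited assignment it removes the event instead: "this AE will neither be counted in tables for solicited AEs nor in tables for unsolicited AEs but in tables for all AEs".

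Protocol 12.7 states the general rule: "However, for missing data in AE evaluation (e.g. missing information about severity or causality) a worst-case approach will be applied".

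The endpoint affected is listed in SAP 1.3.2: "Rate of solicited and unsolicited adverse events (AEs) during the treatment period until day 56". SAP 6.2.2 uses the treatment group total as denominator, and SAP 1.1 plans 12 subjects in each of five groups. Protocol 12.3, in its paragraph on unsolicited AEs, calls for serious AEs to be shown by SOC/PT, grade and relatedness. SAP 2.6 adds Fisher exact tests of AE rates between groups.

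**The concern.** Every AE is either solicited or unsolicited. A blank assignment is a gap in the record and not a third category. Leaving the event out of both sets of tables therefore gives a wrong count in one of them, and the error always runs towards fewer events.

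Two things are at stake. The first is a named secondary endpoint, in groups small enough for one subject to be visible. The second is the display of a serious event. If a related serious AE has a blank assignment, it adds to the overview counts, but no table gives its term. A reader comparing the serious AE count in the overview with the detailed tables and the serious-AE listings would find them disagreeing, with no planned explanation.

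**Working it through.** The plan states no figure on this point, so there is none to reproduce. The check has three steps.

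**1. Where an unassigned AE is shown (SAP 7.1 and 7.2)**

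| Output | Covers | Unassigned AE shown? |
|---|---|---|
| Table 1.4.2, overview counts | all AEs | yes, including the serious and related-serious rows |
| Tables 1.4.3 to 1.4.6, summaries by type | solicited or unsolicited | no |
| Table 1.4.7, maximum severity | all AEs | yes |
| Tables 1.4.8, 1.4.9, 1.4.11, 1.4.12, by symptom | solicited | no |
| Table 1.4.10, maximum severity | solicited | no |
| Tables 1.4.13 to 1.4.20, by SOC/PT | unsolicited | no |
| Tables 1.4.21 to 1.4.24, discontinuation, missed second vaccination, severity | unsolicited | no |
| Tables 1.4.25 to 1.4.27, by causality | unsolicited | no |
| Listings 1.4.3 and 1.4.4 | all AEs | yes; 1.4.3 gives PT, SOC, AE type, seriousness and causality |
| Listings 1.4.11/1.4.12 and 1.4.25/1.4.26, serious AEs | unsolicited; solicited | no |

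Table 1.4.2 is titled for solicited and unsolicited events. I read it as the all-AE table because its rows are not split by type.

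**2. Effect on a rate**

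Inputs: 12 subjects per group and 60 in total (SAP 1.1), and percentages of subjects on the group total (SAP 6.2.2).

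- Ceiling per unassigned AE: 1/12 = 8.3 percentage points in a group, or 1/60 = 1.7 points overall.
- With k unassigned AEs of one class in k different subjects of one group, the ceiling is k × 8.3 points: 0 for k = 0, 8.3 for k = 1, 16.7 for k = 2.
- The rate falls only if the subject has no other counted AE of that class. As an illustration, Protocol 4.4 reports unsolicited AEs in 32.4% of MV-CHIK subjects in MV-CHIK-202 and in 66.7% of subjects in MV-CHIK-101. Take these as the chance p that the subject has another unsolicited AE, and assume independence. The expected fall per unassigned unsolicited AE is (1 − p)/12. This gives 0.676/12 = 5.6 points and 0.333/12 = 2.8 points.

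**3. Effect on a comparison**

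For x/12 against 0/12, the two-sided Fisher exact p-value is 2 × C(12,x)/C(24,x).

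- x = 5: 2 × 792/42,504 = 0.037
- x = 4: 2 × 495/10,626 = 0.093

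One uncounted subject can thus move a two-group comparison across 0.05. This is an illustration only: SAP 2.6 does not say whether the tests are pairwise or across all five groups. The error in a rate is always downward, but the difference between groups can shrink or grow, depending on which group loses the event.

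**The case against.** The best defence is that the event is not hidden. Listing 1.4.3 shows it with its preferred term, seriousness and causality, and its AE type column would show the blank. Table 1.4.2 counts it, and Protocol 10.3 sends serious events to the safety desk within 24 hours whatever the flag says. This stands. A reader might infer that an unassigned serious AE disappears from the report, and the documents do not support that. The gap is confined to the detailed tables and the serious-AE listings.

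A second objection is that the rule does not breach Protocol 12.7. That section names severity and causality as examples, and a worst case has a clear meaning for those and for seriousness. Neither solicited nor unsolicited is the worse class, so there is no obvious worst case to impute. The examples are not exhaustive, so the SAP rule sits uneasily with the protocol's intent, but a flat contradiction is arguable at most.

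Third, part of the gap comes from the table design. A correctly flagged solicited AE also appears in no SOC/PT table and in no table by causality category. That is so, but it does appear in the by-symptom tables, and an unassigned AE appears in none of the three.

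Fourth, the flag may never be missing. Protocol 15.4 describes automatic checks for incomplete entries, queries and investigator certification. This also stands. A reader might try to project a number of lost events from the AE frequency in MV-CHIK-202 and an assumed share of blank flags. The documents give no such share, and those data pool vaccine and control subjects at an interim snapshot.

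**Conclusion.** The point holds and is minor. The rule gives a wrong count whenever it is used, and the planned tables offer no place where the term of an unassigned event would be tabulated. Its size per event is bounded: one rate, by at most 8.3 points in a group, and by nothing if the subject already has another counted AE of that class.

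A reader might infer that both rates are understated. One unassigned AE belongs to one class and can lower only that rate. Both rates can be low only if there are unassigned AEs of both true types.

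The conclusion assumes that the tables are produced as listed in SAP 7.1 and that the SAP 2.8 rule is applied as written. If every flag is completed before analysis, the effect is zero.

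**What to change.** Replace the last sentence of SAP 2.8 with a rule in two stages.

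1. A missing assignment is queried and resolved, at the latest at the Blind Data Review Meeting (SAP 2.9), which precedes unblinding for the preliminary analysis (SAP 2.4).
2. An AE still unassigned is counted as solicited if its term is on a fixed list of solicited symptoms matching the diary and it began within the 7-day diary period after an injection. Otherwise it is counted as unsolicited, including when the start date is too incomplete to decide.

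Footnote the number assigned by default in each group.

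The list must be written into the SAP, because term and date alone do not settle the class from the present text. Protocol 11.7 names nausea, vomiting, headache and fatigue as the diary's systemic symptoms, while Table 6 also grades diarrhoea, myalgia and fever. Protocol 12.3 ties solicited AEs to the diary, and Protocol 10.2 replaces symptoms with a diagnosis once one is known.

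The cost is a short SAP edit and a small derivation, with no new data. The downside is that a few events may be put in the wrong one of the two classes; the footnote shows how many could be.

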2.9 Protocol Deviations

Protocol deviations will be collected only for the preliminary analysis. A listing of the potential protocol deviations will be prepared by Assign Data Management and Biostatistics GmbH using information from the eCRF documentation and monitoring reports. These protocol deviations will be classified into major or minor protocol deviations based on their possible impact on the study results in a Blind Data Review Meeting (BDRM) prior to the preliminary analysis attended by Assign Data Management GmbH and Themis Bioscience GmbH (sponsor).

Major protocol deviations will include but are not limited to the following:

- Subjects with any confirmed immunosuppressive or immunodeficient condition, including human immunodeficiency virus (HIV), hepatitis A, B or C infection or a family history of congenital or hereditary immunodeficiency
- Subjects who received the wrong or no IMP
- Subjects who received less than the protocol-defined number of vaccinations
- Subjects who received a wrong dose other than they were randomized to
- Subjects who entered the study even though they did not satisfy the entry criteria
- Subjects with substantial time window violations on vaccination visits
- Subjects who received an forbidden prior or concomitant medication
 - Immunosuppressive drugs: Use of corticosteroids (excluding topical preparations) or immunosuppressive drugs within 30 days prior to first IMP administration, or anticipated use during the trial
 - Treatments with non-study licensed vaccines within 4 weeks prior to first study vaccination until the end of the treatment period (day 56)
 - Receipt of blood products or immunoglobulins within 120 days prior to the Screening Visit or anticipated receipt of any blood product or immunoglobulin before completion of the treatment period (day 56)
- Further protocol deviations that could impact immune response that have not been described above

Adapted from:

STAT03_A Statistical Analysis Plan

Version 6.0, Effective Date 16-Feb-2018

Confidential and intellectual property of Assign DMB. No part of this document or its contents may be duplicated, referenced, published or otherwise disclosed in any form or by any means without prior written consent of Assign DMB.

Page 12 of 29

06CJDX

These criteria for potential protocol violation are identified at the time of planning the study. However, during the course of the trial unforeseen events may occur or new scientific knowledge may become available, therefore final decisions on whether any protocol violation could impact immune response and thus lead to exclusion from the per-protocol (PP) population will be made by the sponsor on a case by case basis in a blinded manner (and prior to study unblinding).

All protocol deviations will be listed in the analysis and described in the Clinical Study Report (CSR).

It is not planned to define a second PP population prior before database closure since it is not expected that protocol deviations after day 56 affect the primary immunogenicity endpoint. In case of unexpected changes or further protocol deviations documented after the BDRM, it may be discussed in a second DRM prior to database closure which analyses may be repeated for the final analysis.

2.10 Medical Coding

Adverse events and medical history will be coded using MedDRA in the most current version. Concomitant medications and vaccination history will be coded using WHO Drug Reference List and Anatomical Therapeutic Chemical (ATC) Classification System in the most current version.

2.11 Analysis Populations

2.11.1 Safety Population

The safety population is defined to include all subjects who entered into the study and received at least one IMP administration. All analysis based on the safety population will be carried out using the actual treatment received. Subjects with vaccination protocol deviations will be allocated to a treatment group after a case-by-case review in the Blind Data Review Meeting. If a subject received different doses at different visits, the minimum dose received will decide the treatment group.

2.11.2 Modified Intent-to-Treat (mITT) Population

The modified intent-to-treat (mITT) population is defined to include all randomized subjects who receive at least one IMP administration. Subjects will be analyzed according to the treatment group they had been allocated to, rather than by the actual treatment they received.

2.11.3 Per-Protocol (PP) Population

The per-protocol (PP) population is defined as mITT population including subjects with at least one major protocol deviation that might have an impact on the immune response, see [Section 2.9](#). The PP population is the primary population for the immunogenicity analysis and will be defined in the BDRM that is conducted before preliminary analysis.

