12.5.3 Per-Protocol (PP) Population

As a primary analysis, immunogenicity will be assessed on the per-protocol (PP) population. The PP population includes subjects without protocol deviations that could impact immune response. Examples that may lead to exclusion from the PP population are provided here (further criteria may be defined in the SAP):

- Immunosuppressive drugs: Use of corticosteroids (excluding topical preparations) or immunosuppressive drugs within 30 days prior to first IMP administration, or anticipated use during the trial.
- Subjects with any confirmed immunosuppressive or immunodeficient condition, including human immunodeficiency virus (HIV), hepatitis A, B or C infection or a family history of congenital or hereditary immunodeficiency
- Subjects who received the wrong or no IMP

These criteria for potential protocol violation are identified at the time of planning the study. However, during the course of the trial unforeseen events may occur or new scientific knowledge may become available, therefore final decisions on whether any protocol violation could impact immune response and thus lead to exclusion from the PP population will be made by the sponsor on a case by case basis in a blinded manner (and prior to study unblinding). Sample testing issues may also lead to exclusion from the PP population for particular time points.

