1.2.3.1-1.2.3.6	n/a	Repeat tables 2.1.1-x2.1.6 for PP population (if not the same as Safety Population)	
Immunogenicity Results			
Primary Endpoint			
1.3.1.1	2.3.1.1	GMT of anti-Chikungunya PRNT ₅₀ Antibody 28 days after last MV-CHIK vaccination (mITT Population)	
1.3.1.2	2.3.1.2	ANOVA with fixed factor treatment group for GMT of anti-Chikungunya PRNT ₅₀ Antibody 28 days after last MV-CHIK vaccination (mITT Population)	
Anti-Chikungunya PRNT₅₀ Antibody			
1.3.1.3	2.3.1.3	GMT of anti-Chikungunya PRNT ₅₀ Antibody by Visit (mITT Population)	
 • Preliminary Analysis: Visit 1, 3 and 5 • Final Analysis : All available time points
1.3.1.4	2.3.1.4	ANOVA for GMT of anti-Chikungunya PRNT ₅₀ Antibody between treatment groups by Visit (mITT Population)	
 • Preliminary Analysis: Visit 1, 3 and 5 • Final Analysis : All available time points
1.3.1.5	2.3.1.5	Seroconversion rate for Anti-Chikungunya PRNT ₅₀ Antibody by Visit (mITT Population)	
 • Preliminary Analysis: Visit 1, 3 and 5 • Final Analysis : All available time points
Chikungunya-ELISA Antibodies			
1.3.1.6	2.3.1.6	GMT of Chikungunya-ELISA Antibodies 28 days after last MV-CHIK vaccination (mITT Population)	
1.3.1.7	2.3.1.7	ANOVA for GMT of Chikungunya-ELISA Antibodies between treatment groups 28 days after last MV-CHIK vaccination (mITT Population)	
n/a	2.3.1.8	GMT of Chikungunya-ELISA Antibodies by Visit (mITT Population)	
 • All available time points
n/a	2.3.1.9	ANOVA for GMT of Chikungunya-ELISA Antibodies between treatment groups by Visit (mITT Population)	
 • All available time points
n/a	2.3.1.10	Seroconversion rate of Chikungunya-ELISA Antibodies by Visit (mITT Population)	
 • All available time points
Measles-ELISA antibodies			
n/a	2.3.1.11	GMT of Measles-ELISA Antibodies 28 days after last MV-CHIK vaccination (mITT Population)	
 • All available time points

Adapted from:

Page 21 of 29

STAT03_A Statistical Analysis Plan

Version 6.0, Effective Date 16-Feb-2018

Confidential and intellectual property of Assign DMB. No part of this document or its contents may be duplicated, referenced, published or otherwise disclosed in any form or by any means without prior written consent of Assign DMB.

06CJDX

1.3.1.1 - 1.3.1.7	1.3.2.1 - 1.3.2.11	Repeat tables for PP Population	

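### SAP 2.11.3 defines the per-protocol set, the primary immunogenicity set, as *including* major deviators, where the protocol and SAP 2.9 exclude them

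*Combined protocol and SAP*

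**What the plan says.** SAP 2.11.3 says the PP population "is defined as mITT population including subjects with at least one major protocol deviation that might have an impact on the immune response", with a cross-reference to SAP 2.9. It then gives the set its role: "The PP population is the primary population for the immunogenicity analysis and will be defined in the BDRM", the blind data review meeting held before the preliminary analysis.

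Protocol 12.5.3 gives PP the same role ("As a primary analysis, immunogenicity will be assessed on the per-protocol (PP) population") but the opposite content: "The PP population includes subjects without protocol deviations that could impact immune response". Protocol 12.2 also runs the primary comparison of PRNT50 geometric mean titres (GMTs) in PP, and protocol 12.5.2 assigns mITT to the secondary immunogenicity analyses.

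SAP 2.9 lists the major deviations, among them wrong or no product, forbidden immunosuppressants, and "Subjects who received less than the protocol-defined number of vaccinations". It leaves to a blinded case-by-case decision whether a violation "could impact immune response and thus lead to exclusion from the per-protocol (PP) population will be made by the sponsor".

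In SAP 7.1 the two tables under the primary endpoint heading, 1.3.1.1 and 1.3.1.2, have titles ending "Antibody 28 days after last MV-CHIK vaccination (mITT Population". PP appears only in a later row that repeats the tables.

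**The concern.** SAP 2.11.3 is the SAP's only formal definition of the set on which the primary analysis is run, and it contradicts the protocol and another section of the same SAP. Programmers and the data review meeting work from that sentence. Followed as printed, it leaves in the primary analysis of variance the subjects whose titres the plan regards as unreliable, such as someone given the wrong product or treated with immunosuppressants.

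There is also a procedural cost. SAP 2.13 says analyses follow the protocol, but requires departures from the SAP to be described and justified in the study report. A statistician who programs the sensible definition would be departing from the SAP text on the primary population. If the wording is corrected only after unblinding, a reader may ask whether the population was chosen with the results in view.

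The table list does not resolve this. A reader who opens the tables under the primary endpoint heading finds mITT results, although both documents call PP primary.

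**Working it through.** The plan has no power or sample-size figure to reproduce; protocol 12.4 and SAP 1.4 say no formal calculation was made. The only check available is 5 groups × 12 = 60, which agrees. The rest is a comparison of texts, with arithmetic to show scale.

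**1. The texts side by side.**
- Protocol 12.5.3: PP is subjects without impacting deviations.
- SAP 2.9: impacting deviations lead to exclusion from PP.
- SAP 7.2, Listing 1.1: has a column for the reason a subject is not in PP.
- SAP 2.11.3: PP is mITT *including* subjects with such a deviation.

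The first three agree; the fourth does not. It can be read in two ways. If *including* restricts the set, PP is the deviators only. If it merely adds, it adds nothing, because mITT already contains every randomised subject with at least one administration; PP then equals mITT and no planned exclusion takes place.

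**2. Set sizes.** Assume all 60 subjects are treated, so mITT = 60, and let d be the number with an impacting major deviation. The documents give no d; 5–15% of 60 is 3 to 9.

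| d | intended PP (60 − d) | deviators only (d) | PP = mITT |
|---|---|---|---|
| 3 | 57 | 3 | 60 |
| 6 | 54 | 6 | 60 |
| 9 | 51 | 9 | 60 |
| 12 | 48 | 12 | 60 |

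On the deviators-only reading, with all five groups represented, the error degrees of freedom are d − 5: 4 at d = 9 and 1 at d = 6. At d = 3 five groups cannot all be represented.

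**3. Precision, as an illustration.** The half-width of an unadjusted 95% interval for a pairwise GMT ratio, as a multiplicative factor, is 10^(t(0.975, 5n − 5) × SD × √(2/n)), with n per group. The SD of log10 titre is not in the documents; 0.3, 0.5 and 0.7 are assumed. Take d = 10, spread evenly at two per group.

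| Set | n per group | SD 0.3 | SD 0.5 | SD 0.7 |
|---|---|---|---|---|
| PP = mITT | 12 | 1.76 | 2.56 | 3.74 |
| Intended PP | 10 | 1.86 | 2.82 | 4.27 |
| Deviators only | 2 | 5.90 | 19.29 | 63.01 |

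For example, at n = 2 and SD 0.5 the factor is 10^(2.571 × 0.5 × 1) = 19.29. The deviators-only analysis would be useless. The PP = mITT analysis would look slightly more precise than intended, so the harm there is unplanned inclusion rather than lost precision.

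**4. Group E.** SAP 5.2 takes Group E's primary titre at Day 28. Protocol 8.5.3 lists the Visit 3 blood samples before the second injection, which for Group E is placebo, and describes that injection as a vaccination with vaccine or placebo. A Group E subject who misses it could therefore be counted as having too few vaccinations under SAP 2.9, although the primary sample had already been drawn. One such loss is 1/12 = 8.3% of the group.

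**The case against.** The strongest reply is that this is one wrong word whose meaning nobody would mistake. SAP 2.9, to which 2.11.3 refers, speaks of exclusion; the protocol is clear; SAP 2.13 defers to the protocol; Listing 1.1 expects reasons for not being in PP; and membership is settled in a blinded meeting. That stands as evidence of intent. It does not make the printed definition usable, because neither reading of it gives the protocol's set.

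Three stronger inferences are tempting and are not supported.

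- *The primary set is the reverse of the protocol's, and the analysis runs on deviators.* This holds on only one of the two readings, and the other passages point to exclusion as the intention.
- *Group E subjects who miss placebo lose their primary value.* SAP 2.11.3 counts only deviations that might affect the immune response, and SAP 2.9 leaves the decision to case-by-case review. The loss is a risk, not a rule. Some ambiguity remains, because too few vaccinations is a listed major deviation and reviewers blinded to group cannot tell a missed placebo from a missed vaccine dose.
- *The Day 182 and Day 365 PP analyses cannot be cleaned, because nothing about medication or vaccines is recorded then.* Protocol 9.10.2 asks about both at each visit, whereas Table 2 and protocol 9.10.1 stop at Visit 5, so the documents conflict rather than leave a plain gap. Long-term titres are secondary endpoints, for which protocol 12.5.2 uses mITT. The SAP's reason for not defining a second PP set, that "it is not expected that protocol deviations after day 56 affect the primary immunogenicity endpoint", is correct for the primary endpoint, and SAP 2.9 allows a second review meeting.

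The table headings can fairly be called presentational, since the PP repeats are planned. The mismatch still matters while the definition of PP is itself wrong.

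**Conclusion.** The point holds as a contradiction in the written definition of the primary analysis set. SAP 2.11.3 conflicts with protocol 12.5.3 and SAP 2.9, and on either reading it keeps impacting deviators in the primary GMT comparison. It must be corrected, even though it is very likely a drafting slip and nothing shows that the wrong set was analysed.

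The size depends on the number of deviators, which the documents do not give. The wording itself is wrong for any number, but with no impacting deviation the intended PP and mITT sets coincide and the PP = mITT reading would change nothing. The precision figures also rest on assumed SDs, and those for the deviators-only set illustrate the less plausible reading.

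Relabelling the primary tables is a sound alignment of lower weight. The Group E rule is a minor clarification.

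**What to change.** (a) Before the blind data review meeting, replace *including* with *excluding* in the first sentence of SAP 2.11.3 and leave the rest as it stands. The protocol is already right, so no protocol amendment is needed.

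(b) In SAP 7.1, title the PP versions of Tables 1.3.1.1 and 1.3.1.2, and their final-analysis counterparts, as the primary analysis, and the mITT versions as supportive. The PP repeat row reuses the mITT table numbers in its preliminary-analysis column, so distinct numbers would help.

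(c) As a clarification, add a sentence that only deviations occurring before the analysed sample count towards exclusion at that time point. The meeting can then judge each subject's validity at Visit 3 and at Visit 5 while blinded. A Group E subject who misses placebo after the Day 28 sample keeps the primary value; a subject in Groups A to D who misses the second vaccine dose can still be excluded at Day 56.

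All three are SAP text changes with no new data. Separately, protocol 9.10.2 should be reconciled with Table 2 and protocol 9.10.1 on whether medication and vaccinations are recorded after Visit 5. Adding data collection at Visits 6 and 7 would change protocol procedures and need an amendment under protocol 16.1, so it is not part of this correction.
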